- \* Day 1 follow-up visit should only be conducted if there is a safety event identified during or after the kidney biopsy.
- \*\* Every attempt should be made to ensure the second REACT injection is administered 6 months (+ 4 weeks) after the first injection. In the event that the subject cannot schedule his/her second REACT injection 6 months after receiving the first injection, or cannot keep his/her scheduled 6-month visit, ProKidney and the Medical Monitor must be notified immediately. The expectation is that the subject and the clinical center will accommodate the Sponsor's preference that the series of 2 REACT injections should be administered no more than 6 months apart.
  - a. If the screening assessment falls outside of the 60-day window before renal biopsy, re-screening will be performed as described in Screening ([Section 6.1](#)).
  - b. Because the second REACT injection will occur 6 months (+4 weeks) after the first injection, the 6-month visit may not be scheduled.
  - c. In the event that a second REACT injection will not be administered, the subject will undergo all follow-up assessments after the last REACT injection at the 24-month EOS Visit.
  - d. The EOS Visit will take place 24 months after the last REACT injection, or when the subject is terminated from the study by the Investigator ([Section 8.6](#)), or when the subject voluntarily discontinues from the study ([Section 5.4](#)).
  - e. The clinic will perform a urine dip-strip pregnancy test. If positive, then a confirmatory test will be performed by the central laboratory.
  - f. Post-menopausal women with a confirmatory FSH test do not have to undergo pregnancy testing throughout the study.
  - g. Within 48 hours before Days 0 for renal biopsy and REACT injection(s), hemoglobin levels will be verified as > 9 g/dL per site standard practices.
  - h. On Days 0 for renal biopsy and REACT treatment (s), hemoglobin and hematocrit will be measured before and after procedure per site standard practice at the local lab. These samples will be processed by the site's local laboratory to accelerate notification of results and subsequent decisions affecting clinical care. Additionally, blood samples for hemoglobin and hematocrit after procedure will be sent to the central laboratory where results can be entered into the study database.
  - i. Prior to, day of, and day after biopsy and REACT injection(s), microscopic urinalysis will be performed using a dip (test) stick

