### 7.3.3. Hematology

Hemorrhage following biopsy and REACT injection is a known and foreseeable risk to subjects participating in this study. Therefore, hemoglobin and hematocrit will be measured by the site's local laboratory before and after each procedure and compared to baseline levels. Other bleeding parameters (e.g., APTT, PTT-INR, platelets) also will be measured throughout the study.

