### 7.5.2. REACT Injection

Before performing the REACT injection, the operating physician will evaluate the subject as follows:

- Perform a physical examination to determine the feasibility of the procedure.
- Evaluate bleeding parameters, including coagulation panel, PTT-INR, platelets, hemoglobin, hematocrit, and other pertinent laboratory studies.
  - *Note: Hemorrhage following REACT injection is a known and foreseeable risk to subjects participating in this study. Therefore, hemoglobin and hematocrit will be measured before and after each REACT injection per the site's standard practice and compared to baseline levels.*
- Review imaging studies, including ultrasound, MRI, and CT or fluoroscopic CT, to determine route of access, depth of kidney, and appearance of cortical-medullary junction.
- Map potential REACT cell deposition sites.
- Determine classification and associated perioperative /post-operative risk according to the American Society of Anesthesiologists (ASA) with respect to airway assessment, medical history, allergies, and medications.
- Interview the subject and the subject's family/supporters to discuss the procedure, its risks and possible complications. Answer questions and obtain written informed consent.

Prophylactic antibiotics will be given intravenously according to site standard practice. An initial CT scan may be ordered, if necessary, to evaluate adjacent viscera, renal location, and the presence of renal cysts. A CT scan must be used in conjunction with ultrasound to locate the cortical-medullary junction.

REACT is targeted for injection into the kidney cortex via a needle/cannula and syringe compatible with cell delivery. The intent is to introduce REACT via penetration of the kidney capsule and deposit REACT into multiple sites of the kidney cortex. Initially, the kidney capsule will be pierced using a 15- to 20-gauge trocar /access cannula inserted approximately 1 cm into the kidney cortex.

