## 9.7. Safety Analysis

### 9.7.1. Laboratory Evaluations

Baseline values will be collected immediately prior to REACT injection. Observed and change from baseline laboratory data will be summarized via sample size, mean, standard deviation, median, minimum, and maximum for the continuous variables as well as frequency and proportion for the categorical variables. Laboratory abnormalities will be defined using the NCI CTCAE grading scheme. Abnormal laboratory values will be flagged as above or below the normal range. The results of laboratory testing for renal function, specifically sCr, BUN, and urinary albumin, are of particular interest for this study.

The incidence of treatment-emergent laboratory abnormalities, defined as values that increase at least one toxicity grade between baseline and any time post-baseline up to six months following REACT injection, will be summarized. If baseline data are missing, then the latest value between

biopsy and injection will be used as the baseline value. If baseline and pre-injection data are missing, then any graded abnormality (i.e., at least a Grade 1) will be considered as treatment-emergent. These values will be summarized for both the full analysis set and the injection analysis set. Observed and change from baseline values will be presented as descriptive statistics; generating inferential statistics is not planned. These data will be provided in a tabular listing.

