4.7 Baseline Definition

Unless otherwise specified, baseline is defined as the last non-missing value prior to the first REACT injection.

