7.3 Clinical Laboratory Assessments

Measurement of clinical laboratory parameters will be conducted at the time points presented in the [Appendix B](#). For purposes of analyses, laboratory results based upon standardized units will be used.

Results from all clinical laboratory parameters including pregnancy test will be presented in data

listings for the FAS.

For the IAS, a summary of the laboratory parameters at baseline, each scheduled post-baseline visit and change from baseline will be provided by test category (e.g., chemistry, hematology, etc.). Continuous clinical laboratory values will be summarized by presenting descriptive statistics. UACR will be considered as a categorical variable with three categories: <30 mg/g, 30 – 299 mg/g, and \geq 300mg/g. Qualitative results at each time point measured will be summarized by presenting the number and percentage of subjects.

Laboratory assessment results from unscheduled visits will be excluded from table summaries but will be included in data listings. When there are repeat measurements for a given visit (i.e. retests), only the last measurement will be listed and used in the table summaries.

Results that are reported as above or below the limit of quantitation (e.g. <4, >10) will be not be imputed and will be treated as missing values for summarization purposes. The originally reported result (e.g. <4, >10) will be displayed in the listings.

Laboratory abnormalities will be defined using the NCI CTCAE grading scheme. Abnormal laboratory values will be flagged as above or below the normal range.

For the IAS, the incidence of treatment-emergent laboratory abnormalities, defined as values that increase at least one toxicity grade between baseline and post-baseline up to six months following REACT injection, will be summarized. If baseline and pre-injection data are missing, then any graded abnormality (i.e., at least a Grade 1) will be considered as treatment-emergent. These values will be summarized descriptively for the IAS.

Additionally, for the IAS, shift tables (shift from baseline to the worst post-baseline value) will be presented split by the inter-injection, post-second injection period, and the post-injection period as described in [section 4.9](#). Shift tables will describe the shift in CTCAE grades when available, or the shift from low/normal/high when CTCAE grades are not available.

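### Haemoglobin is drawn before and after each procedure, but the SAP's single baseline compares second-injection values with a reference 6 to 7 months old and leaves the biopsy change unsummarised

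*SAP*

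**What the plan says.** Protocol 7.3.3 names haemorrhage after biopsy and injection as an anticipated hazard, and for that reason "hemoglobin and hematocrit will be measured by the site's local laboratory before and after each procedure and compared to baseline levels". Protocol 7.5.2 repeats the rule for the injections: "hemoglobin and hematocrit will be measured before and after each REACT injection per the site's standard practice and compared to baseline levels". Neither section says which baseline is meant. Note h to Table 2 fixes the days: "On Days 0 for renal biopsy and REACT treatment (s), hemoglobin and hematocrit will be measured before and after procedure". It adds that "blood samples for hemoglobin and hematocrit after procedure will be sent to the central laboratory where results can be entered into the study database".

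On the analysis side, SAP 4.7 states that, unless otherwise specified, "baseline is defined as the last non-missing value prior to the first REACT injection". The only separate definition is for vital signs (SAP 7.4), and it too refers to the first injection. For laboratory data on the IAS, SAP 7.3 says "a summary of the laboratory parameters at baseline, each scheduled post-baseline visit and change from baseline will be provided". It also plans shift tables from baseline to the worst value, including one for the post-second injection period. SAP 6.2 counts haemoglobin and haematocrit among the renal-specific laboratory values summarised as raw and change-from-baseline data. For the FAS, laboratory results are listed only.

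**The concern.** The samples form natural pairs around three procedures, and the SAP has a matching reference for only one of them. At the first injection the SAP baseline is the right one. At the second it is a value from before the first injection. For the biopsy there is no change at all, because both values precede baseline.

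This matters because haemoglobin is unlikely to stand still between injections in this population. Entry eGFR is 14 to 20 mL/min/1.73m². Protocol 1.6.5 links CKD with anaemia and reports improved haemoglobin in 3 of 7 Phase 1 subjects after REACT. SAP 5.5 tracks anaemia therapy as a medication category of special interest. A slow decline could look like a bleed at the second injection, and a rise could hide one. Safety is the primary objective, and attribution of AEs is made by investigators in an open-label study, so a clean laboratory summary is a useful cross-check.

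**Working it through.** There is no power or sample-size figure to reproduce: the study is descriptive, with up to 10 subjects and no hypothesis test. The check has four steps.

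**1. Age of the reference at the second injection.** Inputs: injections 6 months apart with a window of +4 weeks (SAP 3.1); pre-injection visit 10 to 14 days before injection (Protocol 6.3); one month = 365.25/12 = 30.44 days.

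Age = interval between injections + days from the baseline draw to the first injection.

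- Interval: 6 × 30.44 = 183 days, up to 183 + 28 = 211 days.
- Baseline drawn on the day of the first injection: 183 to 211 days (6.0 to 6.9 months).
- Baseline from the pre-injection visit: 183 + 10 = 193 days, up to 211 + 14 = 225 days (6.3 to 7.4 months).

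The range is 183 to 225 days, and longer if the second injection is postponed.

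**2. What the second-injection change contains.**

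Reported change = (after second injection − before second injection) + (before second injection − before first injection) = procedural change + drift.

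The documents give no drift figure. The values below are assumptions for illustration, in g/dL:

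| Assumed drift | Reported change if true procedural change is −1.0 | Reported change if true procedural change is 0 |
|---|---|---|
| −1.0 | −2.0 | −1.0 |
| −0.5 | −1.5 | −0.5 |
| 0 | −1.0 | 0.0 |
| +0.5 | −0.5 | +0.5 |
| +1.0 | 0.0 | +1.0 |

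Under these assumptions a real drop of 1 g/dL can be doubled or disappear, and no bleed at all can show as a drop of 1 g/dL.

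**3. The biopsy.** Values before and after the biopsy both precede the first injection. The SAP tables start at baseline, so no biopsy change or shift is calculated. What remains is the FAS listing.

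**4. Whether another planned output supplies the missing comparison.**

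- *Shift tables* (SAP 7.3) take the worst value over a whole period. The post-second injection period runs to withdrawal or completion (SAP 4.9), so a Day 0 to Day 1 drop cannot be isolated. SAP 4.9 defines an acute second injection period, but the laboratory tables do not use it.
- *Treatment-emergent laboratory abnormalities* use the same baseline and a window of six months after an injection that SAP 7.3 does not identify.
- *AE tables* do separate the pre-injection and acute second injection periods (SAP 7.2.5). However, Protocol 8.3 does not require a clinically significant laboratory change to be recorded as an AE unless it is an SAE or leads to discontinuation or withdrawal.
- *Safety ultrasound* abnormalities are tabulated by visit for the FAS (SAP 7.7). This shows bleeding visible on imaging, not the size of a haemoglobin fall.

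**The case against.** The best defence is that bleeding is already well covered. Haemorrhage is singled out as an event of special interest (Protocol 8.1.1.2 and 8.1.1.3). Ultrasound follows the biopsy and each injection, and CT or colour Doppler follows each injection (Protocol 7.4.1 and 7.5.2). Note h says the local values serve prompt clinical decisions, and the protocol nowhere promises a before-to-after analysis. Raw values are tabulated and listed for at most 10 subjects, so a reader could see some of the drift. All of this stands. It makes the point modest, but it does not supply the missing comparison.

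Several stronger readings are tempting and are not supported:

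- *The biopsy drop is not measured.* It is measured, and laboratory results are listed for the FAS. It is not summarised.
- *A biopsy bleed lowers the baseline and so understates the drop at the first injection.* The right reference for that injection is the last value before it, which is the SAP baseline. Nothing is understated.
- *The SAP departs from the protocol without saying so.* Protocol 9.7.1 says "Baseline values will be collected immediately prior to REACT injection" without naming the injection. Its fallback, the latest value between biopsy and injection, fits a first-injection baseline. The two can be read as agreeing, so silence in SAP section 10 is not an omission.
- *The pre-procedure value is lost.* Note h names only the post-procedure sample for the central laboratory. It does not say that the local value stays out of the CRF, and the CRF is not available here. The last-value rule in SAP 7.3 concerns retests, which paired samples are not. Both are points to confirm.
- *Haemoglobin is the only objective measure of bleeding.* Imaging is objective too.
- *One or two drifting values would settle the table.* The SAP also reports the median and quartiles.

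**Conclusion.** The point holds as a gap in a safety summary that is cheap to close. The SAP's single baseline makes second-injection haemoglobin and haematocrit changes a sum of procedural change and drift over 183 to 225 days, and no planned table summarises the biopsy change. The age of the reference follows from the documents. The size of the distortion does not: the span of 2 to 0 g/dL for a true 1 g/dL drop rests on an assumed drift of −1 to +1 g/dL and shows what is possible, not what is likely. The first-injection change is unaffected. The primary endpoint, which counts related AEs, is not altered, and bleeding that is recorded as an AE or seen on ultrasound is still reported.

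**What to change.** In SAP 4.7 and 7.3, define a procedure-specific baseline for haemoglobin and haematocrit: the last value before that biopsy or injection. The reference would then be from the same day or within 48 hours, or at most 14 days old if only a value from the pre-injection visit is in the database.

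Add one table of the change from that baseline to the lowest value through Day 1, with each pair taken from one laboratory:

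- Use the FAS for the biopsy, limited to subjects biopsied in this study, since Protocol 5.4 lets subjects enter with a biopsy from another protocol. The Day 1 visit after biopsy takes place only if a safety event was identified, so for most subjects the Day 0 post-procedure value will be the lowest available.
- Use the IAS for the injections, first and second shown separately.

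State in SAP 7.3 that before and after values are separate time points and not retests. Confirm that the local pre-procedure value is entered in the CRF, and say in the protocol which baseline its before-and-after comparison means.

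The samples are already planned, so no new visits or draws are needed. The cost is minor data entry and one extra table. The existing change-from-baseline tables can stay as they are for longer-term trends.

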4.8 Partial Concomitant Medication (CM) and Adverse Event (AE) Date Handling

For the purpose of inclusion in prior and/or concomitant medication and AE tables, incomplete medication and AE start and stop dates will be imputed as follows:

Partial start dates (where UK, UNK and UNKN indicate unknown or missing day, month and year respectively):

- UK-MMM-YYYY:
 - If the month and year are different from the month and year of the treatment start date, assume 01-MMM-YYYY.
 - If the month and year are the same as the treatment start date month and year, then impute start date as the earliest of treatment start date and end date of CM/AE.
- DD-UNK-YYYY/UK-UNK-YYYY:
 - If the year is different from the year of the treatment start date, assume 01-JAN-YYYY of the collected year.
 - If the year is the same as the treatment start date year, then impute start date as the earliest of treatment start date and end date of CM/AE.

Partial stop dates (where UK, UNK and UNKN indicate unknown or missing day, month and year respectively):

- UK-MMM-YYYY: Assume the last day of the month.
- DD-UNK-YYYY/UK-UNK-YYYY: Assume 31-DEC-YYYY.

[figure not shown]

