4.3 Study Day

Study day 1 will be the day of the first REACT injection. That is, the treatment start date is the date of the first REACT injection. For assessments/events on or after the treatment start date, the

study day is calculated as the date of assessment/event minus the date of treatment start + 1. For assessments before treatment start date, the study day of the assessment is defined as the date of assessment minus the date of treatment start.

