4.9 Analysis Periods

The following analysis periods will be defined as:

- Pre-Injection Period: from the start day of biopsy to the first REACT injection.
- Acute First Injection Period: from the first REACT injection to 1 month following the first REACT injection. The acute first injection period is a subset of the inter-injection period defined below.
- Inter-Injection Period: from the first REACT injection to either the second REACT injection or (if no such second injection was delivered) trial withdrawal or completion.
- Acute Second Injection Period: from the second REACT injection to 1 month following the second REACT injection. The acute second injection period is a subset of the post-second-injection period defined below.
- Post-Second Injection Period: from the second REACT injection to trial withdrawal or completion. This period will not apply to participants for whom only one REACT injection was delivered.
- Post-Injection Period: from the first REACT injection to trial withdrawal or completion. This period includes both the inter-injection and post-second injection periods.

[figure not shown]
If necessary, imputed dates will be used to determine the analysis period for adverse events.

Figure 1. Analysis Period Diagram for Subjects that Received Two Injections

Abbreviations: EOS = End of Study

Figure 2. Analysis Period Diagram for Subjects that Received One Injection

Abbreviations: EOS = End of Study

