7.2.1 Treatment-Emergent Adverse Events

Treatment-emergent adverse events (TEAEs) are defined as any AE that started after the first injection of REACT or started prior to the first injection but increased in severity or frequency after the first injection of REACT. For missing onset or end dates, the rules stated in [Section 4.8](#) will be followed. The imputed dates will be used to determine if the AE is treatment emergent.

In addition to the overall treatment-emergence period defined above, the analysis periods defined in [section 4.9](#) will be used for analysis of the AEs:

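### Partial AE start dates are anchored only to the first injection, so day-unknown events in the second-injection month or the biopsy month go to the wrong analysis period or to none

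*SAP*

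**What the plan says.** SAP 4.3 fixes the reference date: "the treatment start date is the date of the first REACT injection". SAP 4.8 compares partial start dates with that date and no other.

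- **Day unknown, month other than that of the first injection:** "If the month and year are different from the month and year of the treatment start date, assume 01-MMM-YYYY".
- **Day unknown, same month as the first injection:** "then impute start date as the earliest of treatment start date and end date of CM/AE".
- **Month unknown:** the same logic by year, with 1 January as the default when the year differs.

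SAP 4.9 then defines periods that begin at three different procedures: "Pre-Injection Period: from the start day of biopsy to the first REACT injection"; "Acute Second Injection Period: from the second REACT injection to 1 month following the second REACT injection"; "Post-Second Injection Period: from the second REACT injection to trial withdrawal or completion". It adds: "If necessary, imputed dates will be used to determine the analysis period for adverse events". SAP 7.2.1 says the same for treatment emergence: "The imputed dates will be used to determine if the AE is treatment emergent".

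SAP 7.2.5 tabulates AEs, related AEs and SAEs by these periods. Biopsy-related AEs before the first injection are counted in the pre-injection period. SAP 7.2 has AEs recorded from the day of the biopsy onwards. No section gives a separate rule for the second injection or a lower limit at the biopsy date.

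**The concern.** The imputation rule has one anchor, while the periods it feeds have three: biopsy, first injection and second injection. In its own month, the first injection is handled conservatively, because an ambiguous event is placed on the injection date. The other two procedures get no such treatment.

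The second injection is planned 6 months (+4 weeks) after the first, so it never falls in the anchor month. The biopsy usually precedes the first injection by about a month (Protocol 6.2), so it often does not either. In those months every day-unknown event goes to the 1st, which is before the procedure unless the procedure took place on the 1st.

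The two errors differ in consequence. A second-injection event is credited to the wrong sub-period. A biopsy event can receive an onset before AE collection began and so belong to no period. The SAP's primary endpoint covers procedure-related as well as product-related AEs, and biopsy complications are described as procedure-related in Protocol 8.1.1.3.

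**Working it through.** The plan states no figure on this point, so there is none to reproduce. The check applies SAP 4.8 and 4.9 literally.

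**Worked dates (assumed).** Biopsy 10-Mar-2021, first injection 14-Apr-2021, second injection 20-Oct-2021; AE stop date not used.

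| True onset | Recorded | Imputed | Period assigned | Correct period |
|---|---|---|---|---|
| 12-Mar | UK-MAR | 01-Mar | none (before biopsy) | pre-injection |
| 16-Apr | UK-APR | 14-Apr | inter-injection | inter-injection |
| 22-Oct | UK-OCT | 01-Oct | inter-injection | acute second, post-second |
| 28-Nov | UK-NOV | 01-Nov | acute second, post-second | post-second only |

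If biopsy and first injection share a month (01-Apr and 29-Apr), a day-unknown AE of 03-Apr becomes 29-Apr and counts as treatment-emergent. A known stop date of 10-Apr would keep it in the pre-injection period.

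**Share moved before the second injection, given a missing day.** Let L be the mean month length, 1461/48 = 30.44 days, and w the onset lag in days. With the injection day uniform over the month, the event moves when onset is in the same month and the injection was not on the 1st:

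share(w) = (L − w − 1)/L for w ≤ L − 1, otherwise approximately 0.

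For lag uniform on 0 to W, the average is about (L − W/2 − 1)/L:

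- W = 3: (30.44 − 2.5)/30.44 = 92%
- W = 7: (30.44 − 4.5)/30.44 = 85%
- W = 14: (30.44 − 8)/30.44 = 74%
- W = 30: (30.44 − 16)/30.44 = 47%
- lag 1 to 30: (30.44 − 16.5)/30.44 = 46%
- lag 0 to 730 (24 months): the shares sum to about (L − 1)/2 = 14.7 days, and 14.7/731 = 2.0%

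Enumerating four calendar years gives 91.8%, 85.2%, 73.7%, 47.5%, 45.9% and 2.0%. Restricting to the preferred weekdays for the procedures changes nothing material (47.5–47.6% at 30 days). The corresponding share for the first injection is 0%.

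**Movement the other way.** A day-unknown AE that starts 31–60 days after the second injection is set to the 1st of its month, which can lie inside the acute window. In the same enumeration 49% of such AEs enter the acute second period wrongly. Over lags 0–60 days, 24% leave that period and 24% enter it.

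**After the biopsy.** This uses the same kind of enumeration with an assumed biopsy-to-injection gap. Each entry is the share of day-unknown AEs placed in no period / in the inter-injection period.

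| Gap | within 3 days | 7 days | 14 days | 30 days |
|---|---|---|---|---|
| 28 days | 87% / 13% | 81% / 19% | 69% / 31% | 48% / 52% |
| 35 days | 92% / 0% | 86% / 2% | 74% / 11% | 48% / 36% |
| 56 days | 92% / 0% | 86% / 0% | 74% / 0% | 48% / 1% |

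The 30-day entries count only onsets before the first injection.

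**Effect on an incidence.** SAP 7.2.5 divides the number of subjects with the event by the number in the analysis set. With 10 subjects, one subject is 1/10 = 10 percentage points, and more if fewer are treated.

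**The case against.** The strongest reply is that little is lost for the second injection. Treatment emergence depends only on the first injection, and SAP 7.2.5 also tabulates related TEAEs over the whole post-injection period. A reader might infer that the primary endpoint is undercounted for second-injection events. The documents do not support that: a displaced event is still treatment-emergent, still related, and still in the overall table. This part of the reply stands.

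A reader might also infer that the rule always favours the second injection by moving events away from it. That is true of the post-second period as a whole but not of the acute second period, which gains events from the following month about as readily as it loses them. This also stands.

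Third, the percentages apply only when the day is missing. Protocol 8.3 requires a start date for each AE, and Protocol 6.5 sets visits on Days 1 (if discharged on the injection day), 7, 14 and 28, so early post-injection dates should be comparatively well observed. The documents give no rate of missing days.

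Fourth, SAP 7.2.5 lists every AE with its date as collected, and SAP 7.2.3 assesses relationship separately for biopsy, injection procedure and product. With up to 10 subjects a reader could find each misplaced case. That helps an attentive reader but does not correct the tables. For a biopsy event that reaches no period, the listing may be the only place it appears.

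**Conclusion.** The concern holds in a limited form. SAP 4.8 misassigns day-unknown AEs in the second-injection month (unless the injection was on the 1st) and in the biopsy month (unless the biopsy was on the 1st or shares a month with the first injection). Nothing elsewhere in the SAP repairs this.

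For the second injection, the acute-second, post-second and inter-injection splits are wrong and the overall post-injection count is right. For the biopsy, an event can be missing from the pre-injection and biopsy-related tables. It would be treatment-emergent only if it later worsened in severity or frequency.

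Given a missing day, the share of AEs moved before the second injection runs from 92% (onset within 3 days) through 85% (7 days), 74% (14 days) and 46–48% (30 days) to 2% (uniform over 24 months). These figures assume uniform onset within each window and injection dates spread over the calendar. They are not estimates of how many AEs will be misplaced, since the number with a missing day is unknown.

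It would also be too strong to say that each misplaced AE shifts an incidence by 10 points. It does so only when that subject has no other qualifying event in the period, because incidence counts subjects.

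The point deserves correction before database lock because it is cheap and affects how procedure-related safety is displayed.

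**What to change.** Change SAP 4.8 for AE start dates only; the medication rules can stay.

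- **Day unknown, month known:** if the month contains the biopsy, first-injection or second-injection date, impute the start to the latest of those dates that is not after the AE stop date. Otherwise use the 1st of the month.
- **Month unknown:** keep the current rule, but never impute a start earlier than the biopsy date. Do not move these events to the latest procedure in the year, because a biopsy event with a late or missing stop date could then be assigned to the second injection.

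The cost is a few lines of SAP text and code. In the calendar check, the day-unknown rule with the latest procedure taking precedence reduces both main errors to 0%: second-injection AEs placed in the inter-injection period, and biopsy AEs placed in no period.

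Three limits remain. Some AEs that truly preceded the second injection within its month would be attributed to it, conservatively: about 8% (7.6%) of day-unknown inter-injection AEs if onset is uniform, with the second injection at 6 months plus 14 days. Post-biopsy AEs in the first-injection month, including when the biopsy shares that month, would still count as treatment-emergent unless the stop date precedes the injection. Later-month AEs set to the 1st can still be drawn into the acute second period, so its table should carry a footnote counting the events placed there by an imputed date.
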